5.1.3 Subject Exclusion Criteria

The subject must be excluded from participating in the trial if the subject:

- 1. Is currently participating in or has participated in a study of an investigational agent or using an investigational device within 4 weeks of the first dose of treatment.
- 2. Has a diagnosis of immunodeficiency or is receiving systemic steroid therapy or any other form of immunosuppressive therapy within 7 days prior to the first dose of trial treatment.
- 3. Has had a prior monoclonal antibody within 4 weeks prior to study Day 1 or who has not recovered (i.e., \leq Grade 1 or at baseline) from adverse events due to agents administered more than 4 weeks earlier.
- 4. Has had prior chemotherapy, targeted small molecule therapy, or radiation therapy within 2 weeks prior to study Day 1 or who has not recovered (i.e., ≤ Grade 1 or at baseline) from adverse events due to a previously administered agent.
 - Note: Subjects with \leq Grade 2 neuropathy are an exception to this criterion and may qualify for the study.
 - Note: If subject received major surgery, they must have recovered adequately from the toxicity and/or complications from the intervention prior to starting therapy.
- 5. Has a known additional malignancy that is progressing or requires active treatment. Exceptions include basal cell carcinoma of the skin, squamous cell carcinoma of the skin, or in situ cervical cancer that has undergone potentially curative therapy.
- 6. Has known active central nervous system (CNS) metastases and/or carcinomatous meningitis. Subjects with previously treated brain metastases may participate provided they are stable (without evidence of progression by imaging for at least four weeks prior to the first dose of trial treatment and any neurologic symptoms have returned to baseline), have no evidence of new or enlarging brain metastases, and are not using steroids for at least 7 days prior to trial treatment.
- 7. Has an active automimmune disease requiring systemic treatment within the past 3 months or a documented history of clinically severe autoimmune disease, or a syndrome that requires systemic steroids or immunosuppressive agents. Subjects with vitiligo or resolved childhood asthma/atopy would be an exception to this rule. Subjects that require intermittent use of bronchodilators or local steroid injections would not be excluded from the study. Subjects with hypothyroidism stable on hormone replacement or Sjogren's syndrome will not be excluded from the study.
- 8. Has evidence of interstitial lung disease or active, non-infectious pneumonitis.
- 9. Has an active infection requiring systemic therapy.
- 10. Has a history or current evidence of any condition, therapy, or laboratory abnormality that might confound the results of the trial, interfere with the subject's participation

for the full duration of the trial, or is not in the best interest of the subject to participate, in the opinion of the treating investigator.

- 11. Has known psychiatric or substance abuse disorders that would interfere with cooperation with the requirements of the trial.
- 12. Is pregnant or breastfeeding, or expecting to conceive or father children within the projected duration of the trial, starting with the pre-screening or screening visit through 120 days after the last dose of trial treatment.
- 13. Has received prior therapy with an anti-PD-1, anti-PD-L1, anti-PD-L2, anti-CD137, or anti-Cytotoxic T-lymphocyte-associated antigen-4 (CTLA-4) antibody (including ipilimumab or any other antibody or drug specifically targeting T-cell co-stimulation or checkpoint pathways). Patients who have previously received MK-3475 or participated in an MK-3475 clinical trial will be ineligible.
- 14. Has received prior therapy with vorinostat or other epigenetic agent.
- 15. Has a known history of Human Immunodeficiency Virus (HIV) (HIV 1/2 antibodies).
- 16. Has known active Hepatitis B (e.g., HBsAg reactive) or Hepatitis C (e.g., HCV RNA [qualitative] is detected).
- 17. Has received a live vaccine within 30 days prior to the first dose of trial treatment.
- 18. Requires total parenteral nutrition and is unable to swallow pills or unable to take a suspension through a gastrostomy tube.

5.1.4 Inclusion and Exclusion Criteria for Second Course Phase (Retreatment Period for Post-Complete Response Relapse ONLY)

Subjects may be eligible to receive MK-3475 in the Second Course Phase of this study if the study remains open and the subject meets the following conditions:

- Stopped initial treatment with MK-3475 after attaining an investigator-determined confirmed response according to RECIST1.1 response criteria
- Was treated for at least 24 weeks with MK-3475 before discontinuing therapy
- Received at least four treatments with MK-3475 beyond the date when the initial CR was declared
- Experienced an investigator-determined confirmed cutaneous or radiographic disease progression after stopping their initial treatment with MK-3475
- Did not receive any anti-cancer treatment since the last dose of MK-3475

- Have a performance status of 0 or 1 on the ECOG Performance Scale
- Demonstrate adequate organ function as detailed in Section 5.1.2
- Female subject of childbearing potential should have a negative urine or serum pregnancy test within 72 hours prior to receiving retreatment with study medication.
- Female subjects of childbearing potential should be willing to use 2 methods of birth control or be surgically sterile, or abstain from heterosexual activity for the course of the study through 120 days after the last dose of study medication (Reference Section 5.7.2). Subjects of child bearing potential are those who have not been surgically sterilized or have not been free from menses for > 2 year.
- Male subjects should agree to use an adequate method of contraception starting with the first dose of study therapy through 120 days after the last dose of study therapy.
- Does not have a history or current evidence of any condition, therapy, or laboratory abnormality that might interfere with the subject's participation for the full duration of the trial or is not in the best interest of the subject to participate, in the opinion of the treating investigator.

Subjects who restart treatment will be retreated using the same guidelines for the combination of MK-3475 and vorinostat.

Visit and response criteria requirements are outlined in Section 6.1 – Trial Flow Chart for the second course

Patients upon progression might have requested an experimental biopsy to investigate tumor immunology at the time of progression.

5.2 Trial Treatments

The treatment to be used in this trial is outlined below in Table 2.1 This is for initial treatment of patients upon trial entry and similarly for retreatment of patients after progression on a CR.

Drugs	Dose/Potency	Dose Frequency	Route of Administration	Regimen/Treatment Period	Use
1. Vorinostat	400mg	QD 5 out of 7 days per week for 3 weeks (21 days) starting the day of MK-3475 infusion	Oral or via PEG	Maximum of 2 years	Experimental

Table 2.1 MK-3475 in combination with vorinostat

Drugs	Dose/Potency	Dose Frequency	Route of Administration	Regimen/Treatment Period	Use
2. MK-3475	200mg	Q21 days	IV infusion	Maximum of 2 years	Experimental
The MK-3475 dosing interval may be increased due to toxicity as described in Section 5.2.1.2.					

Patients will initiate vorinostat at 400mg daily on the same day as MK-3475 200 mg IV Q21 days infusion. Vorinostat should be taken within 30 minutes of a meal. Vorinostat will be continued 5 out of 7 days throughout each week of the 21 day cycle.

Radiographic imaging (RECIST 1.1 and IrRC) will be completed at a minimum of 9 weeks of starting the MK-3475 and vorinostat combination. Patients who have objective responses or stable disease will continue therapy. Patients who obtain clinical benefit from the combination will be allowed to continue therapy for a maximum of 2 years, or until progression or severe toxicity, whichever comes first.

Patients can be treated for a maximum of 2 cycles before a confirmatory scan for a CR is performed.

Patients who do not achieve a RECIST 1.1 criteria objective response at the first radiographic evaluation can continue the combination of vorinostat and MK-347 provided that they do not demonstrate clinical deterioration (defined by the following parameters and determined by the treating physician):

- 1. Absence of signs and symptoms of disease progression
- 2. No decline in ECOG performance status
- 3. Absence of rapid disease progression
- 4. Absence of progressive tumor at critical anatomical sites (e.g. cord compression) requiring urgent alternative medical intervention.

Patients who receive a confirmed CR on trial may consider discontinuation of treatment. Upon progression they can be retreated on a second course of therapy according to Table 2.1. patients who progress on the second course of therapy are off study.

5.2.1 Dose Selection/Modification

5.2.1.1 Dose Selection

The rationale for selection of dose of MK-3475 to be used in this trial is provided in Section 4.0 - Background and Rationale.

Since MK-3475 will be dosed as a flat dose there will be no requirement to calculate a dose/kg for each patient unless a dose reduction is needed.

The approved dose of vorinostat is 400mg QD for CTCL. However, published clinical experience in additional clinical trials has suggested that dosing at 400 mg 5 out of 7 days reduces toxicity and increases tolerability of the drug compared to daily 400 mg use. Consequently, we propose the 5 out 7 day schedule for this trial.

5.2.1.2 Dose Modifications for MK-3475 and Vorinostat

Toxicity will be graded using Common Terminology Criteria for Adverse Events (CTCAE version 4.0). The protocol will change to CTCAE version 5.0 if is published within the course of the trial.

Because it there may be overlap in the toxicities of both agents, and difficulty in attributing toxicity to either agent, patients experiencing any Grade 3 toxicity (except those outlined in Table 3.1 and Section 5.2.1.4) or any Grade 4 toxicity will have *both MK-3475 and vorinostat held until improvement of the adverse event to Grade 1 or baseline*.

Toxicity that requires more than two dose reductions or modifications of vorinostat will lead to discontinuation of the patient from the treatment phase of the study. *Patients are not permitted to continue on vorinostat or MK-3475 dosing alone.* In addition, no dose re-escalations are allowed during the study period unless toxicities are resolved to grade 1. Justification will be recorded in the source documents

Before initiation of subsequent cycles, each patient will be evaluated for possible toxicities that may have occurred after the previous treatment. All Grade 3 or 4 toxicities

(except those specified in Table 3.1 and Section 5.2.1.4) should resolve to Grade 1 or baseline before re-initiation of study treatment. Dose modification will be made based on the toxicity with the greatest severity.

Toxicity	Grade	Hold Treatment (Y/N)	Timing for restarting treatment	Dose/Schedule for restarting treatment	Discontinue Subject (after consultation with Sponsor)
Hematological Toxicity	1, 2	No	N/A	N/A	N/A
	3* *Excluding Grade 3 neutropenia, anemia, and thrombocytopenia See Section 5.2.1.4)	Yes	Toxicity resolves to Grade 0-1 or baseline	May increase the dosing interval by 1 week	Toxicity does not resolve within 12 weeks of last infusion Permanent discontinuation should be
	4	Yes	Toxicity resolves to Grade 0-1 or baseline	May increase the dosing interval by 1 week	considered for any severe or life-threatening event
Non-hematological toxicity	1	No	N/A	N/A	N/A

Toxicity	Grade	Hold Treatment (Y/N)	Timing for restarting treatment	Dose/Schedule for restarting treatment	Discontinue Subject (after consultation with Sponsor)
 Note: Exception to be treated similar to grade 1 toxicity Grade 2 alopecia Grade 2 fatigue For additional information regarding Adverse Events with a potential Immune-Etiology reference Section 5.6.1.1. and Appendix 12.8 	2	Consider withholding for persistent symptoms	Toxicity resolves to Grade 0-1 or baseline	Clinical AE resolves within 4 weeks: Same dose and schedule (reference Section 5.6.1.2 for recommendations regarding pneumonitis) Clinical AE does not resolve within 4 weeks: May increase the dosing interval by 1 week for each occurrence	Toxicity does not resolve within 12 weeks of last infusion
	3, 4	Yes	Toxicity resolves to Grade 0-1 or baseline	May increase the dosing interval by 1 week for each occurrence	Toxicity does not resolve within 12 weeks of last infusion Permanent discontinuation should be considered for any severe or life-threatening event

In case toxicity does not resolve to Grade 0-1 within 12 weeks after last infusion, trial treatment should be discontinued. With investigator and Sponsor agreement, subjects with a laboratory adverse event still at Grade 2 after 12 weeks may continue treatment in the trial only if asymptomatic and controlled. For information on the management of adverse events, see Section 5.6.1.

Subjects who experience a recurrence of the same severe or life-threatening event at the same grade or greater with re-challenge of MK-3475 should be discontinued from trial treatment.

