2.1.2.1 Safety assessments during the Phase II expansion

This investigator initiated study will be under the oversight of the Fred Hutchinson/University of Washington Cancer Consortium IRB and Data and Safety Monitoring committee. The investigators are ultimately responsible for monitoring the safety of patients who have entered this study and for alerting the Consortium IRB to any event that seems unusual in accordance with IRB policy. The investigator is responsible for the appropriate medical care of patients during the study. The investigator remains responsible to follow, through an appropriate health care option, adverse events that are serious or that caused the patient to discontinue before completing the study. The patient should be followed until the event resolves or stabilizes. Frequency of follow-up is left to the discretion of the investigator.

Safety measurements that will be used in the study include physical examinations and clinical laboratory tests (hematology and blood chemistries). The adverse event will be graded for toxicity using the NCI CTC version 4.0. Toxicity assessment will occur at the start of each cycle, or more frequently if clinically indicated. Any adverse events leading to a treatment interruption or dose reduction along with all adverse events that are grade 3 and higher will be recorded in the CRF. Adverse Events that meet Merck's definition of Event of Clinical Interest (refer to the Pembrolizumab ECI guidance document) will also be recorded.

The criteria for dose de-escalation for adverse events are outlined in Section 5.2. Any patient who requires two dose modifications or de-escalations will be taken off study.

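### The vorinostat re-escalation rule in Section 5.2.1.2 can be met by recovery off drug, so a required reduction may be reversed before the lower dose has been tried

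*Combined protocol and SAP*

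**What the plan says.** Section 5.2.1.2 contains the only sentence on raising a dose again: "no dose re-escalations are allowed during the study period unless toxicities are resolved to grade 1". It is followed by "Justification will be recorded in the source documents". No period, number of doses or observation on the reduced dose is attached.

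For any Grade 4 toxicity, and any Grade 3 toxicity outside the listed exceptions, the same section has "both MK-3475 and vorinostat held until improvement of the adverse event to Grade 1 or baseline". Section 5.2.1.4.2 repeats this for Grade 3/4 diarrhea and for severe nausea, vomiting or dehydration. Section 5.2.1.5 lets a new cycle start once non-hematologic toxicity is at Grade 1 or less, or at baseline.

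Section 5.2.1.3 lists events after which a change of vorinostat dose is mandatory. They include Grade 4 non-hematologic toxicity, Grade 3 non-hematologic toxicity persisting beyond three days, and Grade 3/4 laboratory values needing treatment or leading to hospitalization. The tables there step down by 100 mg at a time, from 400 mg or, in the fallback regimen, from 300 mg.

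**The concern.** A mandatory reduction rests on the view that the previous dose was too much for that patient. A rule on reversing it should ask for evidence that the patient tolerates the lower dose. Here it asks only for a grade that the patient must normally reach anyway, with both drugs stopped, before restarting. Recovery during a hold shows that the event was reversible. It does not show that the event stays away on 300 mg, still less on 400 mg.

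What is at stake is re-exposure to the dose that preceded a severe event before the lower dose has had a fair trial. Safety and tolerability of a combination with no earlier clinical experience is the primary objective (Sections 3.1 and 4.2.3).

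**Working it through.** The plan gives no figure to reproduce. The check is a comparison of rules, followed by simple dose arithmetic.

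**Scope.** Non-hematologic Grade 3/4 events that require a vorinostat reduction and allow restart. Three kinds of event fall outside because they end MK-3475 or all trial treatment: Grade 3 enterocolitis (5.2.1.4.2), Grade 3/4 pneumonitis (Table 7) and Grade 3/4 infusion reactions (Table 5). Where MK-3475 ends, vorinostat ends too: "Patients are not permitted to continue on vorinostat or MK-3475 dosing alone".

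**The conditions side by side.**
- To restart: the event at Grade 0-1 or baseline, reached while both drugs are held.
- To re-escalate: toxicities at Grade 1, plus a recorded justification.

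A patient who restarts at Grade 0-1 with nothing else above Grade 1 satisfies the second grade condition by satisfying the first. No reduced dose has yet been taken.

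**Where the condition still binds.**
- Another toxicity is above Grade 1, such as a Grade 2-3 cytopenia through which dosing continues.
- The patient restarts at a baseline above Grade 1.
- Treatment restarts after a Grade 4 cytopenia at the thresholds in 5.2.1.4.1.
- A laboratory event continues at Grade 2 after 12 weeks by agreement.
- Treatment continues by agreement without recovery after a 12-week delay.

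**Within a cycle.** Section 5.2.1.5 allows either drug's dose or schedule to be adjusted as needed. It does not mention re-escalation. Section 5.2.1.2 would ordinarily govern, but no cross-reference says so.

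**Doses per cycle** (5 doses a week):
- 21 days: 5 × 3 = 15
- 28 days: 5 × 4 = 20
- 35 days: 5 × 5 = 25

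**Illustration: re-escalation after one week (an assumed timing).**
- 21-day cycle, 400 to 300 mg. Full dose: 15 × 400 = 6,000 mg. Full reduced cycle: 15 × 300 = 4,500 mg (25.0% lower). With re-escalation: 5 × 300 + 10 × 400 = 5,500 mg (8.3% lower). Share of the reduction undone: (5,500 − 4,500) / 1,500 = 67%.
- 28-day fallback, 300 to 200 mg. Full dose: 20 × 300 = 6,000 mg. Full reduced cycle: 20 × 200 = 4,000 mg (33.3% lower). With re-escalation: 5 × 200 + 15 × 300 = 5,500 mg (8.3% lower). Share undone: (5,500 − 4,000) / 2,000 = 75%.

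These percentages describe dose, not harm.

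**Cost of requiring one reduced cycle, against immediate re-escalation** (one level, 100 mg per dose):
- 21 days: 15 × 100 = 1,500 mg
- 28 days, including a 21-day cycle lengthened by a week under Table 3.1: 20 × 100 = 2,000 mg
- 28-day cycle lengthened to 35 days: 25 × 100 = 2,500 mg

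Over an assumed six unextended cycles (6 × 6,000 = 36,000 mg), the first is 1,500 / 36,000 = 4.2% of planned vorinostat. For the 28-day fallback it is 2,000 / 36,000 = 5.6%. A two-level reduction (200 mg per dose) doubles the milligram figures, and a repeated cycle adds to them.

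**The case against.** The strongest reply is that the sentence is a prohibition with an exception. Grade 1 is necessary but entitles nobody to a higher dose. Re-escalating on the day of restart would cancel a reduction that 5.2.1.3 makes mandatory, and an investigator would have to justify that in writing. This stands as a limit on the risk. It does not supply a criterion, because the content of the justification is left open.

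There are also real safeguards.
- Table 10 (Section 7.2.4) requires advance approval by the clinical monitor for rechallenge after a serious, possibly drug-caused event, or where re-exposure adds significant risk. Vorinostat is supplied by Merck (9.1) and fits the Merck product definition in 7.2, so many events in scope would be covered. The text concerns re-exposure and does not mention dose level.
- Section 5.2.1.2 says treatment should stop on "recurrence of the same severe or life-threatening event at the same grade or greater with re-challenge of MK-3475". This acts only after a second severe event.
- Section 5.2.1.2 also says permanent discontinuation should be considered for any severe event, and staff review adverse events weekly (10.6).
- The number of reductions is capped. Section 5.2.1.2 has "Toxicity that requires more than two dose reductions or modifications of vorinostat will lead to discontinuation", while Section 2.1.2.1 has "Any patient who requires two dose modifications or de-escalations will be taken off study". Neither addresses reversal.

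One could also read resolution as meaning resolution on the reduced dose. The text does not say so. If that was the intent, the amendment only states it.

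Finally, documented discretion is a legitimate design choice, and one cycle is a threshold taken from visit timing rather than safety data. That is fair, and it is a reason to keep the importance modest.

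**Conclusion.** The point holds within its scope. After a non-hematologic Grade 3/4 event that requires a vorinostat reduction and allows restart, the stated grade condition for re-escalation can already be met at restart. The protocol does not require the reduced dose to be tried first. This rests on reading the condition literally and on a patient at Grade 0-1 with no other toxicity above Grade 1.

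A reader might infer more than the documents support:
- That patients may return to full dose at once without restraint. The default is a bar, a justification is required, and serious events need approval for rechallenge.
- That the Grade 1 condition never matters. It still binds in the situations listed above.
- That the run-in result is compromised. DLTs are counted by their occurrence in cycle 1, so re-escalation does not change the count.
- That exposure could exceed plan. The dose never goes above the starting dose.

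Frequency cannot be estimated from the documents, so the expected harm cannot be sized. This is a cheap improvement of modest importance.

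**What to change.** Keep the present sentences in Section 5.2.1.2 and add:

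*After a required reduction, vorinostat is restarted at the reduced dose and may be re-escalated only after at least one full cycle at that dose without recurrence above Grade 1 (or baseline) of the toxicity that led to the reduction; other toxicities must meet the existing condition, with Grade 2 fatigue and alopecia handled as in Table 3.1.*

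In Section 5.2.1.5, add to the within-cycle adjustment sentence: *except re-escalation, which follows Section 5.2.1.2*.

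One cycle fits the existing schedule, since "Toxicity assessment will occur at the start of each cycle, or more frequently if clinically indicated": one scheduled assessment on the reduced dose is then complete before any increase. Tying the test to the causal toxicity keeps an unrelated minor event from blocking re-escalation through the new requirement.

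The amendment should leave alone whether a reversed reduction counts towards the cap. Sections 2.1.2.1 and 5.2.1.2 state different limits, and those need reconciling first.

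The change needs no extra visits, tests or patients. The price is less investigator discretion and a minimum, not a maximum, of one cycle at the lower dose, with the milligram cost shown in the working.
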